#### 10) Monitoring issues

TOF data measured on the GE NMT monitoring device, which currently uses GE's old algorithm, will be sent to GE without randomized arm information to derive corrected TOF (TOFc) based on GE's proprietarty new algorithm. Per correspondence with [name], Principal Engineer at GE Healthcare, he states, "We have made improvements to the TOF algorithm, as its limitations are well known and published. Whereas the old TOF algorithm counted twitches based on their magnitude only, the new algorithm takes both the magnitude and the fade into account. The new algorithm is not published yet and will be in the next Carescape monitor release." Patients with substantial disagreement between TOF and TOFc measurements will be considered as having monitoring issues. Agreement is defined by the proportion of measurements that are perfectly aligned between TOF and TOFc. A second definition for agreement will be the proportion of measurements with a TOF and TOFc difference of <2 twitches. Cases with agreement <80% will be considered a substantial disagreement. We may consider a more stringent threshold for substantial disagreement, for example, agreement <90%.

In addition to those with substantial disagreement between TOF and TOFc (described above), the following patients will also be identified as having monitoring issues:

- 1. Patients with bedside TOF measurements in the operating room but no TOF data available for correction to TOFc
- 2. Patients with incorrect stimulus electrode placement determined by saved images reviewed by GE

Patients with monitoring issues have TOF measurements with varying levels of noise interference, which distinguishes them from patients with, "6) Equipment failure of the neuromuscular train of four monitoring device," which have no TOF measurements. All patients with monitoring issues will be included in the intention-to-treat analyses. Additional analyses based on monitoring issue status are summarized in section 14.0 Study participants that meet the removal criteria above will have their cases reviewed. These cases will be reviewed by an independent panel of surgical and anesthesiology investigators to ensure that the event is not associated with or caused by visibility during the surgery prior to their removal from the study. Any event determined to be due to visibility will be reported to IRB.

#### 14.0 BIOSTATISTICS

In this single-blinded prospective randomized study, patients will be randomized in 1:1 ratio to two arms: moderate NMB (control) or deep NMB (intervention). The two primary endpoints of interest in this study are: levels of IAP and postoperative pain. Thus, in the sample size calculation below, we consider multiple primary endpoints and power the trial to detect success in at least one endpoint. The first primary endpoint of interest is IAP. The second primary endpoint of interest is Pain scores within 6-hours post operation. To characterize the entire set of a patient's IAP measurements under insufflation, we consider the use of area under the curve (AUC). We plan to randomize 130 patients to moderate or deep NMB arms, stratified by BMI (< vs >=30) and surgeon, and expect 120 patients to be evaluable for each of the two primary endpoints. Patients are considered evaluable for the first primary endpoint (IAP) if they can provide at least one IAP recording; patients are considered evaluable for the second primary endpoint (Pain) if they can provide at least one NPS pain score within the 6-hours postoperation.

AUC is a useful clinical endpoint for the aggregate effect over time and can summarize the average response to treatment over the period of observation. AUC is an appropriate summary measure for data collected over time, and it is commonly seen in pain measurements, as well as chronic obstructive pulmonary disease (COPD), diabetes, and pharmacokinetics studies. For this study, we will use the area under the IAP curve during insufflation as a measure for the first primary endpoint which focuses on the effect of deep NMB on IAP during robotic prostactetcomy. We will consider the time-weighted measure of AUC that integrates serial

2.1

assessments of the patient's IAP measurement over time using the trapezoidal rule. The corresponding "mean AUC" (AUCmean) is obtained as AUC/duration of insufflation for each patient. From **Kim et al**, mean IAP decreased by approximately 22% (standard deviation [SD] = 1.3) from moderate NMB to deep NMB.

For the second primary endpoint based on postoperative pain, we will collect all NPS pain scores within the 6-hours postoperation and will express results as AUCpain at the patient level. In a retrospective analysis of 37 patients from a similar population (See Section 3.8), mean pain level within the 6-hours postoperation was 1.3 (SD of 0.5) on the **log-transformed NPS scale**.

Sample size calculation is based on the mean AUCIAP and AUCpain within 6-hours postoperation across patients in each arm. We power this study with 2 primary endpoints to detect 20% decrease in IAP (from 13.9 to 11.1, SD of 4) and 25% decrease in pain scores within the 6-hours postoperation (from 1.3 to 0.975; SD of 0.5) with deep vs moderate NMB, with type I error rate of 0.025 for each endpoint. The change in NPS scores (25% or 1 point on the raw scale) is a validated clinically meaningful change. The decrease in pain scores on which the sample size estimate is based on the natural log transformed scores. This calculation assumes independence of the two primary endpoints. We elected to increase the standard deviation of the AUCIAP in this power calculation as a conservative measure because the population from the reference study is different from the population of interest. A total of 120 patients evaluable for each of the primary endpoints will provide 90% power to detect a significant difference in at least one of the two endpoints. This sample size also allows for an interim analysis halfway through enrollment, using O'brien-Fleming boundaries with Lan de Mets spending functions for futility. We base the interim analysis decision rule on both of the primary outcomes. The trial will continue to full enrollment if the interim analysis results for either/both of the primary outcomes reports p<0.755. The trial may be terminated if p>0.755 for both outcomes. We will conclude that the arms are significantly different if p≤0.025 for either of the outcomes. In order to ensure at least 120 patients evaluable for each of the primary endpoints, we plan to randomize at least 130 patients (See Section 13.0 for potential perioperative scenarios).

Analysis of the primary endpoint which involves IAP will be AUCIAP compared between the two arms using the linear mixed-effects model: randomized arm as the fixed-effect, BMI as the adjustment covariate, with surgeon-level random effects. Transformation of the outcome may be applied if the normality-of-errors assumption is violated. As a secondary analysis, the longitudinal IAP measurements will be analyzed using linear mixed-effects models including time and randomized arm as fixed-effects with stratification variable (BMI), and patient-level random effects, nested within surgeons. In the rare case that the patient's IAP is beyond 15 the surgeon will be unblinded to the IAP, and only the IAP up to the point of unblinding will be included in the analysis. 15 is the conventional goal for the upper limit of IAP at MSKCC. Investigators request they know the IAP at a level of 15, so they can weigh risk/benefit of continuing to operate at that higher threshold of IAP. In this rare occurrence, patients will still be included in the analyses as modified intent-to-treat, including IAP values until IAP-unblinding.

Analysis of the second primary endpoint will be AUCpain within 6-hours postoperation. AUCPain analysis will be conducted with linear mixed-effect model with appropriate transformation for the outcome for normality. The model will include randomized arm as fixed-effects along with stratification variable (BMI), and patient-level random effects, nested within surgeons.

For the primary analyses, all recorded IAP will be analyzed in a modified intent-to-treat fashion. Where a patient randomized to moderate NMB crosses over to deep NMB, all recorded IAP will be analyzed under the randomized arm. As a secondary analysis of the primary outcome, we will perform an as-treated analysis where the set of IAP values will be assigned to the actual intervention received. Correlation between AUCIAP and AUCPain will be summarized using Spearman correlation coefficient. Additionally, the primary endpoints will be summarized between patients with and without neuromonitoring issues (see

Section 13.0). As a sensitivity analysis, planned analyses of both primary endpoints will be repeated after excluding patients with neuromonitoring issues (see Section 13.0).

Although the occurrence will probably be rare, accidental unblinding will be recorded as a protocol violation as part of standard reporting procedure. According to the ICH E9 Statistical Principles for Clinical Trials, usually of violations that occur post-randomization, it is appropriate to include the data from such subjects in the analysis, consistent with the modified intention-to-treat principle. We will include these cases in the primary analysis of the primary outcome in the randomized arm. For each case of major protocol violation, we will enroll an additional patient randomized and included in the analyses. Also, we will perform per protocol analysis that excludes patients who had accidental unblinding.

Surgeon assessment of surgical conditions (continuous measure, on a 1 to 5 scale) recorded every 30 minutes, will be analyzed with linear mixed-effects models as above.

Estimated blood loss (EBL) will be compared between the two arms using linear mixed-effects model (randomized arm and BMI fixed-effects variables, and surgeon-level random effect), accounting for duration of surgery if necessary (i.e., rate of EBL). Transformation of the outcome may be applied if the normality-of-errors assumption is violated.

Postoperative pain (surgical and shoulder pain, 0 no pain to 10 worst pain imaginable), defined at postoperative 1-hour, 6-hour, 12-hour, 24-hour, and 48-hour post operation will be compared between the two arms using linear mixed-effects models with appropriate transformation for the outcomes for normality.

The model will include patient-level random effects (nested within surgeons), treatment arm, and time as fixedeffects, along with stratification variable (BMI) as adjustment factors. To address potential confounding due to history of chronic pain, patients with chronic pain will be excluded from protocol. Chronic pain will be defined as a patient on a sustained-release opioid in the last 3 months. Besides patient-reported pain scores, perioperative analgesia use will be analyzed similarly to the pain scores: intraoperative cumulative IV analgesia use will be compared between the two arms after adjusting for duration of surgery; while postoperative IV analgesia use will be analyzed as cumulative total dose within the first 6-hours post surgery and until prior to discharge (with adjustment for duration of postoperative stay in the analysis).

Postoperative nausea (measured at the same intervals) will also be analyzed with linear mixed-effects models. To address potential confounding due to preoperative risk for nausea, the model will include adjustment for preoperative Apfel score (4 point scale with a maximum of 3 points due to an all male patient population) and preoperative EMEND use. In addition to patient-reported nausea scores, postoperative antiemetic use will be analyzed in the following fashion: the use of any antiemetics will be analyzed with a mixed-effects logistic regression model, and the use of any antiemetics within the first 6-hours post surgery and until prior to discharge will be analyzed with linear mixed-effects models. Time to first rescue antiemetic medication will also be recorded and compared between the two arms using Kaplan-Meier approach and log-rank test.

We will assess the relationship between the treatment arms and operating time (defined as the time between incision to surgery end) using a linear mixed-effects model with transformation for the outcome for normality. The model will include treatment arm and stratification variable (BMI) and surgeon-level random effect

Richmond Agitation Sedation Scale (RASS) scores, measured at 1, 6, 12, 24 hours postperatively will be modeled and compared between the two arms using linear mixed-effects model. The model will include treatment arm and stratification variable (BMI) and surgeon-level random effect.

One primary concern from deep paralysis is postoperative pulmonary complications and the need for reintubation and prolonged postoperative intubation. All patients who receive neuromuscular blockade are at 23

risk of residual paralysis at the conclusion of surgery. Patients who experience residual paralysis from inadequate neuromuscular blockade may experience postoperative pulmonary complications such as respiratory distress, aspiration, and pneumonia, ultimately requiring reintubation and prolonged postoperative intubation. The likelihood of respiratory complications and risk for reintubation are not expected to be different between the two arms. *This risk is independent of the dose or timing of rocuronium administration.*NSQIP data reported 0.82% respiratory complications and 0.47 pulmonary emboli/DVT for 1.29% complication risk from postoperative pulmonary complications. If one or more patients requires reintubation, experiences respiratory distress, aspiration or pneumonia among the first 45 elligible patients (≥2.2% incidence rate) regardless of treatment arm, the trial will be paused for the investigators to assess whether the complication was attributable to the intervention prior to restarting the trial. The incidence of 30-day postoperative pulmonary complications will be recorded and summarized by treatment arm. Postoperative pulmonary complications for recording are defined as the need for reintubation, respiratory distress, aspiration, and pneumonia.

For descriptive purposes, we will assess and the accuracy of surgeon's best guess as to which arm a given patient was assigned. This will allow us to assess blinding success. Similarly, all requests by surgeon to change IAP intraoperatively will be recorded and summarized separately by arm using descriptive statistics.

Reintubations will be limited to any intubation that occurs within the first 24 hours postoperatively.

Respiratory distress is defined by tachypnea to a respiratory rate greater than 30, OR desaturation of 10% or greater from baseline spO2. (either criterion alone will satisfy definition)

Aspiration is defined by pharyngeal or gastric contents below the vocal cords. This must be confirmed by suctioning of pharyngeal or gastric contents from the trachea, fiberoptic bronchoscopy or the finding of a new infiltrate on CXR within 24 hours postop.

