#### 3.7 Area under the curve (AUC)

AUC is a useful clinical endpoint for the aggregate effect over time and can summarize the average response to treatment over the period of observation. AUC is an appropriate summary measure for data collected over time, and it is commonly seen in pain measurements, as well as chronic obstructive pulmonary disease (COPD), diabetes, and pharmacokinetics studies. For this study, we will use the AUC of patient-reported pain numeric pain scale (NPS) scores during the first postoperative hour as a measure for our first primary endpoint and area under the IAP curve during insufflation as a measure for our second primary endpoint. The numeric pain scale (NPS) is a subjective measure which can be used in recovery rooms to assist in the assessment of pain. Individuals rate their pain on an eleven-point scale. The scale is composed of 0 (no pain at all) to 10 (worst imaginable pain).

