#### Summary

Because of the limited number of studies, the true impact of deep NMB on postoperative pain and IAP remains unresolved. Focused clinical trials are required so clinicians can improve patient care and recovery using approaches based on high quality evidence. This is of particular interest to robot-assisted surgery because even with the explosive increase in robotic surgery volume, the effects of deep NMB on these surgical conditions have never been studied.

In this study, our first primary endpoint is to compare the effects of deep (intervention) vs. moderate (control) NMB on postoperative pain on patients undergoing robotic prostatectomy. Additionally, since during robotic surgery, the abdominal IAP is controlled by the surgeon, we hypothesize that with deep NMB the surgeon will accomplish improved surgical exposure and will tolerate lower IAP20. Thus, our second primary endpoint is to investigate if surgical IAP levels will be different when a moderate or a deep NMB technique is used. Secondary endpoints will include evaluation of surgical operating conditions (as assessed by the Leiden scale) and the impact of deep NMB on post-op shoulder pain, post-op nausea, blood loss, and operating time.

At MSK we find ourselves in a priviledged position because we have the capability to handle large volumes of patients and operate with state of the art equipment; clinicians at MSKCC practice with an ethical commitment to generate high quality RCTs.

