#### 13.0 CRITERIA FOR REMOVAL FROM STUDY

Criteria for removal of subject from the study will include patient death, surgical conversion from robotic to open procedure, intraoperative deterioration in clinical condition that would end a planned procedure.

Patients are considered evaluable for the first primary endpoint (IAP) if they can provide at least one IAP recording; patients are considered evaluable for the second primary endpoint (Pain) if they can provide at least one NPS pain score within 6-hours after surgery. Study data will be analyzed according to a modified intention-to-treat principle ("modified" because patients considered inevaluable for a given primary endpoint will be excluded from the analysis of that endpoint).

The following are a list of possible perioperative scenarios. We expect these to occur extremely infrequently. We anticipate fewer than 10 occurrences during the study period and have planned the protocol accordingly.

- 1) Cancelled surgery
  - Patient will not provide either primary endpoint therefore patients in this category will be excluded from primary analysis
- 2) Patient death
  - For patients who die in the perioperative period, any data up until patient death will be analyzed. These patients may possibly contribute data for only one of the two primary endpoints (IAP)
- Surgical conversion from robotic to open procedure
   Any data up until conversion will be analyzed.

   These patients may possibly contribute data for only one of the two primary endpoints (IAP)
- 4) Intraoperative deterioration in clinical condition that would end planned procedure For patients who experience deterioration in clinical condition that ends planned procedure, any data up until deterioration will be analyzed.
  - However, there will be an investigation to assess the possible (but extraordinarily unlikely) influence of protocol in leading to deterioration.
- 5) Deviation from protocol by giving additional dose of NMB to satisfy surgeon request for better visualization
  - All data in this scenario will be analyzed.. Secondary analysis will be conducted as treated.
- 6) Equipment failure of the neuromuscular train of four monitoring device
  Any data up until failure of neuromuscular train of four monitoring device will be analyzed.patient will
  be considered evaluable for only one of the two primary endpoints (IAP).
- Accidental unblinding of surgeon
   All data will be analyzed.. This will be an evaluable patient.

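### The pain primary endpoint has a 1-hour window in Section 3.7 and a 6-hour window in Sections 13 and 14, and Section 14 does not define a usable pain AUC for every evaluable patient

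*Combined protocol and SAP*

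**What the plan says.** **Window.** Section 3.7 uses the AUC of NPS "scores during the first postoperative hour as a measure for our first primary endpoint". Section 14 says: "The second primary endpoint of interest is Pain scores within 6-hours post operation". Section 13 applies the same 6 hours when it defines who is evaluable, and the sample size in Section 14 is built on 6-hour pain data.

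**Evaluability.** Section 13 requires "at least one NPS pain score within 6-hours after surgery". Section 14 repeats the rule: "at least one NPS pain score within the 6-hours postoperation".

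**Construction of the AUC.** For IAP, Section 14 names the trapezoidal rule and gives a mean AUC that "is obtained as AUC/duration of insufflation for each patient". For pain it says only "we will collect all NPS pain scores within the 6-hours postoperation and will express results as" an AUC for each patient. It gives no divisor and no rule for a single score.

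**Model.** The Section 14 model for the IAP AUC has surgeon-level random effects. The model for the pain AUC has arm and BMI as fixed effects and patient-level random effects nested within surgeons, with no time term.

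**Timing.** Section 4.1 schedules pain scores at hours 1 and 6 within the window and defines PACU time as arrival in the PACU. Sections 13 and 14 count 6 hours from the end of surgery or operation without saying which recorded time starts the clock.

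**The concern.** A significant result on pain alone is enough to declare the arms different, so this endpoint should be computable from the text without choices by the analyst. At present it is not.

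- The current text holds two windows for one primary endpoint.
- A patient with one score must be analysed, but the trapezoidal area over zero width is 0 and its logarithm does not exist. The analyst must either drop the patient, against the evaluability rule, or invent a value.
- Without a divisor, two patients with the same constant pain get different areas if their scores cover different spans. At a constant NPS of 4, the area is 4 over 1 hour, 20 over 5 hours and 24 over 6 hours.
- The pain model asks for a variance component that one value per patient cannot supply.

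**Working it through.** **Inputs.** From Section 14: pain 1.3 to 0.975 on the natural-log scale, SD 0.5; IAP 13.9 to 11.1, SD 4; type I error 0.025 per endpoint; 120 evaluable patients, 1:1, so 60 per arm. Sidedness is not stated; two-sided is taken. Section 3.8 gives the pilot: median 4, quartiles 3 and 5, log mean 1.3, SD 0.5.

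**1. The plan's own power** (noncentral t, 118 df, critical value 2.270).
- Pain: 0.325 / (0.5 × √(2/60)) = 3.560, power 90.0%.
- IAP: 2.8 / (4 × √(2/60)) = 3.834, power 94.0%.
- At least one, under the plan's independence assumption: 1 − 0.100 × 0.060 = 99.4%.

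The stated 90% therefore reproduces as the power for pain alone. That is the reference below.

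**2. Scale of the planning values.** exp(1.3) = 3.67 and exp(0.975) = 2.65, a drop of 1.02 points. This agrees with Section 14: "The change in NPS scores (25% or 1 point on the raw scale". The inputs are thus on the scale of a time-averaged score.

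**3. Undivided area, fixed span.** Over exactly 6 hours the means become 6 × 3.67 = 22.02 and 6 × 2.65 = 15.91. On the log scale, 3.092 − 2.767 = 0.325, the planned difference, with the SD still 0.5. A common span costs nothing.

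**4. Undivided area, varying span.** Variation in the log of the span adds to the SD. The documents give no distribution of spans; uniform is assumed.

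| Assumed span | SD of log span | Total SD = √(0.25 + that²) | Pain-alone power |
|---|---|---|---|
| 5–6 h | 0.053 | 0.503 | 89.6% |
| 4–6 h | 0.117 | 0.513 | 88.3% |
| 3–6 h | 0.198 | 0.538 | 84.9% |
| 1–6 h | 0.479 | 0.692 | 61.9% |

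The schedule of hour 1 and hour 6 implies a span near 5 hours, so the first two rows are the relevant ones. The last two show only how far the spans would have to depart from schedule to matter.

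**5. One-score patients.** The documents give no count; all counts here are assumed.
- Dropped: with 1, 3 or 6 per arm lost (59, 57 or 54 left), pain-alone power is 89.4%, 88.3% or 86.3%.
- Coded as zero area: 3 of 60 per arm, simulated with lognormal scores at the planning values and a 5-hour span. Power falls from 86% to 78% if the area is untransformed, and from 90% to 36% on log(area + 1).

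**6. Random effect.** With one value per patient, patient and residual variance enter the likelihood only as their sum. On simulated data (120 patients, 6 surgeons assumed), splitting a total of 0.25 as 0/0.25, 0.05/0.20, 0.125/0.125, 0.20/0.05 or 0.249/0.001 gave the same REML log-likelihood (25.008), arm estimate (−0.342) and standard error (0.092) every time. The component cannot be identified, and the treatment comparison does not depend on it.

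**7. At least one endpoint.** In the worst case in step 5, 1 − (1 − 0.36) × 0.060 = 96%. In the 4–6 hour case it is 1 − 0.117 × 0.060 = 99.3%.

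**The case against.** The strongest reply is that Section 14 governs, Section 3.7 is background, and a competent analyst would infer a 6-hour time average. Section 14 describes AUC as a summary of average response, and its inputs are on the NPS scale. Much of this stands: it is why the cost is small and why Section 3.7 is the text to change. It does not supply a value for a one-score patient, and it leaves a primary endpoint to inference.

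A reader might go further in several directions that the documents do not support.

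- **That an undivided area would not be the effect the trial was powered for.** Step 3 shows that a fixed 6-hour span keeps the log difference at 0.325. Only varying spans cost anything.
- **That the hour-6 score falls outside the window**, because it is timed from PACU arrival while Section 13 counts from surgery. The documents do not fix the origin, and the natural reading is one clock with hour 6 included. The gap is the missing statement. Nor do the documents show that one-score patients will be common, since the PACU flowsheet may hold further scores.
- **That the log scale breaks down for patients with no pain at all.** The log is a planning scale; Section 14 leaves the analysis transformation open, and pilot quartiles of 3 and 5 give no sign that such patients are frequent.
- **That the order of the endpoints matters.** The Section 3 summary says "our first primary endpoint is to compare the effects of deep (intervention) vs. moderate (control) NMB on postoperative pain", while Sections 13 and 14 put pain second. Each endpoint has its own 0.025 and there is no hierarchy, so nothing follows from the label.

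It is also fair that the margin from 120 to 130 patients would absorb part of any drop-out loss, and that the random effect biases nothing. The latter may still stop the model from fitting as written.

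**Conclusion.** The point holds and should be fixed, with a modest expected effect. The current text gives two windows for the pain endpoint, no valid value for some patients who must be analysed, no divisor for pain, and an unidentifiable variance term.

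If data come in near schedule, pain-alone power stays between about 86% and 90%. This rests on the plan's inputs, two-sided testing, and assumed spans and counts. A serious loss would need short spans or one-score patients coded as zero. The plan prescribes neither, but it does not rule out the zero coding.

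Two windows might suggest an inflated type I error. No section permits testing both, so that does not follow. Power for at least one endpoint stays above the stated 90% in every case near schedule and with one-score patients dropped or coded as zero.

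**What to change.** - **Section 3.7:** change the pain window to 6 hours.
- **Section 14, definition:** define pain AUC as the trapezoidal AUC of all NPS scores within 6 hours, divided by the time from first to last score. A patient with a single score takes that score as the mean.
- **Sections 13 and 14, origin:** state one time origin for the window. PACU arrival is already defined in Section 4.1. Say explicitly that the scheduled hour-6 score is included.
- **Section 14, model:** use surgeon-level random effects only for the pain AUC, as for the IAP AUC. The repeated-score models keep the patient-level term.

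The planning values then apply directly and pain-alone power stays at 90.0% with 60 per arm. The cost is wording in three sections, with no new data and no change in sample size. One downside should be acknowledged: a mean over a short span, or a single score, may not represent the full 6 hours.

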# Pain Score from Initial Assessment, Post-operative **Nursing Note**

[figure not shown]

Figure 1. Patient-reported pain scores following robotic prostactectomy.

Pain in the immediate postsurgical period was measured in a recent pilot study. Investigators evaluated VAS pain scores for the first six postoperative hours in 37 patients undergoing robotic prostatectomies between January and March 2018. The results revealed a median VAS score of 4 (25th, 75th percentile: 3, 5) which represents moderate pain on the original scale, and mean of 1.3 (SD=0.5) on the natural log transformed scale. This preliminary evidence shows a high incidence of moderate to high pain score not only shortly after surgery, but also several days post discharge. For this reason it is incumbent on perioperative clinicians (i.e. anesthesiologists) to evaluate and consider any intervention that may lessen the pain burden of patients undergoing these procedures.

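### The 90% power given for success on at least one primary endpoint does not follow from the plan's own inputs, which give 99.4%; power for each endpoint alone is not reported.

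*Combined protocol and SAP*

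**What the plan says.** Section 14.0 sets out to "power the trial to detect success in at least one endpoint". Each endpoint is tested "with type I error rate of 0.025 for each endpoint", and the decision rule reads: "We will conclude that the arms are significantly different if p≤0.025 for either of the outcomes". The planned IAP effect is 13.9 to 11.1 with an SD of 4. The planned pain effect is a "25% decrease in pain scores within the 6-hours postoperation (from 1.3 to 0.975; SD of 0.5" on the natural-log scale). On the joint behaviour of the endpoints the section says: "This calculation assumes independence of the two primary endpoints". It concludes that 120 evaluable patients, allocated 1:1, "will provide 90% power to detect a significant difference in at least one of the two endpoints". It gives no power for IAP alone, pain alone or both.

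The section justifies the pain effect as follows: "The change in NPS scores (25% or 1 point on the raw scale) is a validated clinically meaningful" change. The pilot in Section 3.8 supplies the log mean of 1.3 and SD of 0.5. On the raw scale it reports: "The results revealed a median VAS score of 4 (25th, 75th percentile: 3, 5").

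**The concern.** When either of two independent endpoints can carry the trial, the chance of at least one success must exceed the power of the stronger endpoint. A 90% figure for that rule would mean clearly lower power on each endpoint: about 68% each if the two were equal, since 1 − √0.10 = 0.684. The stated effects, SDs and 60 patients per arm look too favourable for that, so the figure and its label appear not to belong together.

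The stake is interpretation rather than validity. IAP and pain are separate primary objectives with separate hypotheses (Section 2.0). The trial may well succeed on IAP and find nothing on pain. Power for at least one endpoint does not help in reading that result. A reader who takes the 90% literally could dismiss a null pain result as underpowered when, for the effect the plan used, it was not.

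**Working it through.** **Inputs, all from Section 14.0.** 120 evaluable at 1:1, so n = 60 per arm; alpha 0.025 per endpoint; IAP difference 13.9 − 11.1 = 2.8, SD 4; log pain difference 1.3 − 0.975 = 0.325, SD 0.5; independent endpoints. Two-sided testing is assumed, because the decision rule speaks of a difference between arms.

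**Method.** Unadjusted two-sample t-test with 118 degrees of freedom; critical value 2.270; noncentrality = d × √(n/2) = d × √30.

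**Power per endpoint, two-sided**
- IAP: d = 2.8/4 = 0.70; noncentrality 3.834; power 94.0%.
- Pain: d = 0.325/0.5 = 0.65; noncentrality 3.560; power 90.0%.

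**Power for the success rule, under independence**
- At least one: 1 − (1 − 0.9396)(1 − 0.8999) = 1 − 0.0604 × 0.1001 = 0.994.
- Both: 0.9396 × 0.8999 = 0.846.

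The stated 90% is therefore reproduced only as the power for pain alone. A simulation of 20,000 trials agreed: 0.941 for IAP, 0.897 for pain and 0.994 for at least one.

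**Can another reading recover 90%?**

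| Variation | Power for at least one |
|---|---|
| One-sided 0.025 per endpoint (IAP 96.7%, pain 94.2%) | 99.8% |
| Two-sided 0.0125 per endpoint | 98.5% |
| Correlation 0.3 (normal approximation) | 98.7% |
| Correlation 0.5 (normal approximation) | 98.0% |
| Correlation 0.8 (normal approximation) | 96.3% |
| Correlation 1 (normal approximation) | 94.4% |

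Whatever the correlation, the probability of at least one success cannot be smaller than that of the likelier one, so the floor is the IAP power: 94.0% by t-test, 94.4% by the normal approximation.

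**Futility rule.** Stopping needs p > 0.755 on both endpoints at half enrollment (30 per arm). Two-sided, that means |z| < 0.312. The expected z values are 0.70 × √15 = 2.711 for IAP and 0.65 × √15 = 2.517 for pain, so the chances are about 0.007 and 0.011. Their product under independence is about 0.00008. Under any dependence the joint chance cannot exceed the smaller one, about 0.7%. In simulation at correlation 1, the rule lowered at-least-one power only from 94.4% to 94.2%.

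**Sample size that would match the label.** By t-test, 34 per arm (68 evaluable) gives 90.3% for at least one and 33 per arm gives 89.3%. The distance from 120 is too large to be rounding.

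**The pain effect.** 1.3 × 0.75 = 0.975, so the 25% was taken off the log mean. Back-transformed, exp(1.3) = 3.67 and exp(0.975) = 2.65: a fall of 1.02 points and a ratio of exp(−0.325) = 0.723, or 27.7% lower. A 25% lower geometric mean is a log difference of ln(4/3) = 0.288, which is also 1 point from the pilot median of 4.

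| Pain effect (SD 0.5) | Log difference | Two-sided power | One-sided power |
|---|---|---|---|
| As powered, 27.7% lower | 0.325 | 90.0% | 94.2% |
| 1 point from 3.67, ln(3.669/2.669) | 0.318 | 88.6% | 93.3% |
| 25% lower | 0.288 | 81.0% | 87.8% |

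Even with the 25% effect, two-sided power for at least one endpoint is 1 − 0.0604 × 0.1904 = 98.9%.

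**The case against.** The best defence is that nothing in the trial changes. The error is conservative, and 120 patients give about 90% or more on each endpoint with the plan's own inputs. The number is probably right for the weaker endpoint and only its label is wrong; read as a minimum, it is even true. All the inputs are printed, so a reader can compute power per endpoint, and a null result would be read mainly from its confidence interval.

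Most of this stands, and it limits the point to a correction of the text. It does not make the sentence right: the plan claims a specific power for a specific rule, and that power is more than 9 percentage points away from what its inputs give. A mislabel is the simplest explanation, but the plan does not state the derivation. Leaving readers to work out power for two separate primary objectives is a poor substitute for stating it.

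On pain, the defence notes that the log scale is disclosed and that the powered effect, 3.67 to 2.65, is almost exactly the 1-point benchmark. That is correct, and power for 1 point from 3.67 is still 88.6%. What remains is narrow: the effect is called 25% when on the raw geometric-mean scale it is 27.7%, and the plan treats 25% and 1 point as the same thing.

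**Conclusion.** The concern holds. On the plan's inputs, power for at least one significant endpoint is 99.4%, not 90%, with two-sided tests and independence. It is 99.8% one-sided, and no correlation takes it below about 94%. Power is 94.0% for IAP, 90.0% for pain and, under independence, 84.6% for both. Sample size, alpha and the decision rule are unaffected. The secondary point on the pain label also holds but is minor.

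These figures rest on 60 evaluable patients per arm, the printed SDs and an unadjusted t-test. The planned BMI-adjusted mixed model is not modelled, because the plan gives no further variance inputs. Sidedness is an assumption, and the conclusion is the same either way.

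**What to change.** Keep the sample size and rewrite the power statement in Section 14.0 along these lines:

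- With 120 evaluable patients (60 per arm) and a two-sided 0.025 test per endpoint, power is 94% for IAP (2.8 mmHg, SD 4) and 90% for pain (log difference 0.325, SD 0.5).
- Power for at least one endpoint is 99.4% under independence, and about 94% or more at any correlation.
- The pain effect is a 27.7% lower geometric mean, about 1 point from 3.67. If a 25% fall is kept as a benchmark, give its power as well: 81% two-sided, or about 88% one-sided.

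State the sidedness. If one-sided tests are intended, use 96.7%, 94.2% and 99.8% for IAP, pain and at least one endpoint.

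The cost is one paragraph, with no change to sample size, alpha, decision rule or analysis.
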